13.3 Statistical analysis

Statistical analysis will be performed by the study team and [name], Public Health England, Colindale. Differences between groups at each time point will be assessed using Fisher exact test and between time points within groups by McNemar test.

14. Study quality and Management procedures

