6.6 The optimal and safe dose of the inoculum

Based on the previous *N. lactamica* work it is estimated that 50% of volunteers will be colonised 1-2 weeks after inoculation with 10^5 cfu without any safety concerns (Deasy, Guccione et al. 2015). The hypothesis is that those who are colonised at day 4 will exhibit seroconversion by day 14, confirming biologically 'significant' colonisation.

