13.1 Endpoints of the study

Primary endpoint

- Rise in serological specific antibody titre comparing day 0 versus day 14 and 28 days post eradication and comparing early (day 4) versus late (day 14) eradication

Secondary endpoints:

- Assessment of colonisation – culture of *N. lactamica* from throat swabs at day 4 for group 1 and days 4, 7 and 14 for group 2
- Assessment of eradication – culture of *N. lactamica* from throat swabs on the day of eradication, one day, 10 days and 28 days after eradication
- Rise in mucosal specific antibody titre comparing day of screening versus day 14 and 28 days post eradication and comparing early (day 4) versus late (day 14) eradication
- Change in nasal cytokine profile comparing day 0 versus day 4, 14 and 28 days post eradication and comparing early (day 4) versus late (day 14) eradication
- Difference in environmental shedding between short (group 1) and longer (group 2) periods of colonisation.

Safety endpoints:

- Occurrence of unsolicited adverse events within the study period
- Occurrence of serious adverse events within the study period

Safety analysis will be carried out for all volunteers that received the inoculum, regardless of whether or not they complete the study.

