13.2 Sample size

The previous experimental *N. lactamica* challenge study showed a significant rise in serological antibody titre against *N. lactamica* over 2 weeks (Deasy, Guccione et al. 2015). This gave SDs on a log-10 scale of 0.11 for IgA saliva and 0.26 for serum total IgG. For this study, using the SD of 0.26 we will be able to confirm a 4 fold rise with 10 carriers of *N. lactamica* with 90% power using analysis of variance.

Allowing for a drop out rate of approximately 10%, we will therefore recruit volunteers until we have 11 individuals colonised for each group up to a maximum of 22 volunteers for each group. At a dose of 10^4 colony forming units (cfu), long lasting colonisation with *N. lactamica* is easily induced in 35-65% of participants. We showed that increasing the inoculum to 10^5 cfu increased the subsequent carriage of *N. lactamica* to 50% (Evans, Pratt 2011). Therefore approximately 44 individuals will be enrolled. Assuming a screening failure rate of 5%, we will need to screen approximately 46 potential participants to achieve colonisation in 11 of each group.

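### The analysis section names only tests for yes/no data, but the primary endpoint is a quantitative titre rise and the 90% power rests on analysis of variance; the primary analysis needs to be specified.

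*Combined protocol and SAP*

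**What the plan says.** Section 13.3 is the whole statistical analysis section. Its only sentence on method reads: "Differences between groups at each time point will be assessed using Fisher exact test and between time points within groups by McNemar test". It gives no alpha, model, transformation or analysis set.

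Section 13.1 defines the primary endpoint as "Rise in serological specific antibody titre comparing day 0 versus day 14 and 28 days post eradication", and adds a comparison of early with late eradication. Mucosal titres and nasal cytokines are secondary endpoints of the same quantitative kind. Colonisation and eradication, judged by throat-swab culture, are yes/no.

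Section 13.2 works on the log scale: "This gave SDs on a log-10 scale of 0.11 for IgA saliva and 0.26 for serum total IgG". It then says that "using the SD of 0.26 we will be able to confirm a 4 fold rise with 10 carriers" is possible "with 90% power using analysis of variance", and recruits "until we have 11 individuals colonised for each group up to a maximum of 22 volunteers for each group".

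The nearest thing to a yes/no immune outcome is in section 6.6, which hypothesises that "those who are colonised at day 4 will exhibit seroconversion by day 14". Seroconversion is not defined there or elsewhere, and it is not an endpoint in 13.1.

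**The concern.** Fisher's test and McNemar's test cannot be applied to titres until each titre is turned into a yes or a no. The plan gives no rule for doing so. Either the two tests are meant for titres, and the cut-off is missing, or they are meant only for culture results, and the primary endpoint has no planned analysis. On both readings the method behind the sample size is absent from the analysis section.

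Section 3.5 says the trial is to show whether a short containment gives enough immunogenicity before a later study with a genetically modified strain. A non-significant result from an insensitive between-group test could be taken as support for the short period. A ratio with a confidence interval would show which differences the data exclude. Volunteers choose their group and nobody is blinded (section 5.3), so a cut-off or time point left open until the data are seen is a further weakness.

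**Working it through.** **Inputs.** From section 13.2: SD 0.26 on the log10 scale, a 4-fold rise, 10 carriers, 90% power, analysis of variance. Because 11 colonised volunteers are sought in each group to allow for dropout, 10 is read as a per-group number.

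**Assumptions.** Alpha is not stated; two-sided 0.05 is used. Log10 rises are taken as normal. Section 13.2 does not say whether 0.26 is the SD of a titre or of a change. If it is a titre SD and visits are uncorrelated, the SD of a change is 0.26 × √2 = 0.368, so the range 0.26 to 0.37 is shown. All cut-offs below are illustrative, since the plan has none.

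**The plan's own figure.** The effect is log10(4) = 0.602. For two groups of 10, analysis of variance is the two-sample t-test, with noncentrality 0.602 / (0.26 × √(2/10)) = 5.18 on 18 degrees of freedom. Power is 99.8%, or 93.3% at SD 0.368. For a within-group rise by paired t-test it is above 99.9%, or 99.5% at SD 0.368. The stated 90% is therefore not reproduced at 10 per group, but it errs on the safe side. The nearest match is 5 per group, at 89.2%.

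**Between groups, Fisher's test.** A volunteer counts as a responder if the log10 rise exceeds a cut-off c, so the responder probability is 1 − Φ((c − mean)/SD). Power is the sum of the binomial probabilities of all 10 v 10 outcomes with Fisher p ≤ 0.05. A search over c puts the best cut-off midway between the two group means.

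| True difference in rise | SD | t-test | Fisher, best cut-off | Responders at that cut-off |
|---|---|---|---|---|
| 4-fold | 0.26 | 99.8% | 91% | 12% v 88% |
| 4-fold | 0.368 | 93% | 61% | 21% v 79% |
| 2.5-fold | 0.26 | 90% | 54% | 22% v 78% |
| 2.5-fold | 0.368 | 63% | 26% | 29% v 71% |

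The best cut-off cannot be known in advance. With mean rises of 1-fold and 4-fold, SD 0.26 and a 4-fold cut-off, the cut-off sits at the higher mean. The responder rates are then 1% and 50%, and Fisher's power is 58%.

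To show how coarse the test is: 10/10 v 5/10 gives p = 0.033, but 10/10 v 6/10 gives p = 0.087.

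**Within groups, McNemar's test.** If response means a fold rise from day 0, nobody can be a responder on day 0. All changes then run one way, and the test no longer asks a sensible question. Taken at face value, the exact test with 10 pairs needs 6 one-way changes: 2 × 0.5^6 = 0.031, while 2 × 0.5^5 = 0.0625. With a true mean rise of 4-fold and a 4-fold cut-off, half respond, and P(at least 6 of 10) = 37.7%.

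**Culture endpoints.** Fisher and McNemar do fit these. But McNemar asks only whether status changed; it does not estimate how often ciprofloxacin clears carriage. That needs a proportion with an exact interval. If everyone is cleared, the lower 95% limit is 0.025^(1/11) = 71.5% for 11/11 and 0.025^(1/22) = 84.6% for 22/22.

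**The case against.** The strongest reply is that the named tests may still be adequate. A reader might infer from the mismatch that the trial will not have its stated power. The documents do not support that: without a cut-off, power under Fisher or McNemar cannot be derived from them. At the protocol's own 4-fold effect and SD 0.26, Fisher's test reaches 91% if the cut-off happens to lie midway between the group means. This part of the reply stands. It also stands that the 2.5-fold difference and the 4-fold cut-off are illustrations and not the protocol's planning values, and that 10 per group is ample for a 4-fold effect analysed as continuous.

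A reader might also count six primary tests (two time points, each with two within-group rises and one between-group comparison) and infer a false-positive risk of 1 − 0.95^6 = 26.5%. That does not hold for this plan. The tests share baselines and volunteers, so they are not independent. Fisher's test at 10 v 10 has an actual size of about 1% (0.8% to 1.3% for responder rates of 20% to 80%), not 5%. Section 4.1 also makes short versus longer carriage the primary objective, so the lead comparison can be identified. The time point is what remains open.

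Finally, section 11.4 already commits to recording how well treatment clears colonisation in 24 hours. What eradication lacks is a denominator and an interval.

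None of this supplies an analysis for the titre endpoint.

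**Conclusion.** The point holds. The tests in 13.3 match neither the quantitative primary endpoint in 13.1 nor the analysis of variance behind 13.2, and no cut-off bridges the gap. The 90% therefore does not carry over to the analysis as written. In every case checked, the power of the named tests is below that of a continuous analysis. For Fisher at its best cut-off, the loss is about 9 to 33 percentage points for a 4-fold difference and 36 to 37 points for a 2.5-fold difference.

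These sizes rest on two-sided 0.05, 10 carriers per group, normal log10 rises and an SD between 0.26 and 0.37. They do not show that the trial is too small or that 90% power is out of reach; the documents leave the power of the named tests undetermined. Because the primary endpoint has no usable planned analysis, this should be put right before any titre data are analysed.

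**What to change.** Rewrite section 13.3 as follows.

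- **Primary analysis.** Compare early with late eradication on log10 specific serum IgG among carriers, at one named time point and a stated alpha, by ANCOVA with day-0 log10 titre as covariate. Report a ratio with 95% CI. In naming the time point, note that day 14 is the same time since inoculation in both groups, whereas 28 days after eradication is day 32 in one and day 42 in the other.
- **Within-group serum rises (secondary).** Paired t-test on log10 titre, reported as geometric mean fold rise with CI.
- **Mucosal titres and cytokines.** Same approach, with the baseline actually collected: day 0 for saliva and nasosorption, screening for nasal wash, which Tables 10.1 and 10.2 do not schedule on day 0.
- **Culture results.** Keep Fisher and McNemar here. Report eradication as the proportion culture-negative one day after treatment among those culture-positive on the eradication day, with exact CI.
- **Sample size (13.2).** State alpha, and whether 0.26 is the SD of a titre or of a change.

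If the sponsor prefers a responder analysis, the cut-off must be defined in advance and the power recomputed for it. The cost is protocol wording only: day-0 blood is already scheduled for everyone in both groups, and no extra volunteers or samples are needed.

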3.5 General overview

This study will compare the effect of short (4 days) versus longer (14 days) periods of nasal carriage of *N. lactamica* on immunogenicity and confirm the efficacy of oral eradication therapy with ciprofloxacin. Healthy adult volunteers will receive a nasal inoculation of *N. lactamica* and eradication therapy will be given on day 4 or 14. This information will be used to inform the design of future research into the colonisation kinetics and immunogenicity of related organisms. Specifically, the Medical Research Council has funded us to inoculate humans with genetically modified *N. lactamica*. Before designing the protocols for that study we need to know whether a short containment of the volunteers will be sufficient for immunogenicity, and how quickly we can discharge the volunteers after ciprofloxacin eradication. A wild-type strain of *N. lactamica* Y92-100 will be used for this study, selected because we have previously used it safely in experimental challenge of over 340 human volunteers. The same strain is the parent strain for the GMO work described above.

4. Objectives

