4.1 Primary objective

- To compare the effect of short (4 days) versus longer (14 days) oropharyngeal carriage on systemic and mucosal humoral immunogenicity following nasal inoculation with *Neisseria lactamica*

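### The early v late comparison is meant to inform whether short carriage is sufficient for immunogenicity, but the plan offers only a test for a difference, with no interval, margin or definition of sufficient

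*Combined protocol and SAP*

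**What the plan says.** **Purpose.** Section 3.5 gives the reason for the study: "Before designing the protocols for that study we need to know whether a short containment of the volunteers will be sufficient for immunogenicity".

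**Primary objective (4.1).** "To compare the effect of short (4 days) versus longer (14 days) oropharyngeal carriage on systemic and mucosal humoral immunogenicity".

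**Primary endpoint (13.1).** The rise in specific serum antibody titre is assessed from day 0 to day 14 and to 28 days after eradication, and is also compared between early and late eradication. The endpoint therefore has a within-group and a between-group part.

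**Hypothesis (6.6).** The one immunogenicity hypothesis in the document is within-group: "those who are colonised at day 4 will exhibit seroconversion by day 14". No titre threshold for seroconversion is given.

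**Sample size (13.2).** "using the SD of 0.26 we will be able to confirm a 4 fold rise with 10 carriers", with 90% power by analysis of variance. Recruitment runs to 11 colonised volunteers per group, allowing about 10% drop-out, with a cap of 22 inoculated per group.

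**Analysis (13.3).** "Differences between groups at each time point will be assessed using Fisher exact test"; changes over time within a group are to be tested by McNemar's method. Nothing else is specified: no alpha, interval, margin, analysis set or rule linking a result to the question in 3.5.

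**Allocation (5.3).** There is no randomisation or blinding, and volunteers may state a preference for early or late eradication.

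**The concern.** If sufficient means not materially worse than 14 days of carriage, a test for a difference points the wrong way. Rejecting the null would show that short carriage is worse (or better). Failing to reject shows only that the data did not settle the matter, and that outcome becomes more likely as carriers become fewer. Replacing Fisher's test with a t-test or analysis of variance on log titre would not cure this, because the missing element is a bound on how much response may have been lost.

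At stake is the design of the next study, with the genetically modified organism. If a non-significant comparison were taken as support for short containment, a real loss of response after 4 days could be carried into that design unnoticed.

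**Working it through.** **Inputs from the plan (13.2).** SD 0.26 log10 for serum IgG; 10 evaluable carriers per group (11 less about 10%); target effect 4-fold, log10(4) = 0.602.

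**Assumptions.** Two-sided 5%. The plan does not say whether 0.26 is the SD of single titres or of rises, so two values are used for the SD of the rise: 0.26, and 0.26 × √2 = 0.368 (shown as 0.37), which applies if 0.26 describes single, uncorrelated titres. Responder rates are assumed because no responder definition is given.

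**1. The plan's own figure.** For a two-group t-test, the standard error of the difference is SD × √(2/n) and the non-centrality is the effect divided by it.
- 10 per group, SD 0.26: SE = 0.26 × √0.2 = 0.1163; non-centrality 0.602/0.1163 = 5.18; power 99.8%.
- 10 per group, SD 0.368: SE 0.1644; non-centrality 3.66; power 93.3%.
- Within-group rise, 10 carriers: above 99.9% if the SD of the change is 0.26, and 99.6% if it is 0.368.
- 5 per group, SD 0.26: 89.2%.

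The stated 90% is matched only by reading 10 carriers as 10 in total. Read as 10 per group, which is how 13.2 goes on to use it, the claim is conservative. It concerns a 4-fold effect, however, and does not address how small a loss could be excluded.

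**2. Chance that a t-test on log10 titre misses a real deficit in group 1** (10 per group, 18 df, critical value 2.101)

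| True deficit | log10 | Non-centrality, SD 0.26 | Missed | Non-centrality, SD 0.37 | Missed |
|---|---|---|---|---|---|
| 1.5-fold | 0.176 | 1.51 | 70% | 1.07 | 83% |
| 2-fold | 0.301 | 2.59 | 31% | 1.83 | 59% |
| 3-fold | 0.477 | 4.10 | 3% | 2.90 | 22% |

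**3. Chance that Fisher's test, as 13.3 specifies, misses a deficit.** This is by exact enumeration of all outcomes with 10 per group: 90% v 60% responders, 85%; 90% v 50%, 70%. An observed 9/10 v 5/10 gives p = 0.14, with a 95% CI for the difference (group 1 minus group 2) from about −68 to 0 percentage points. Part of this insensitivity comes from reducing titres to yes/no, which is a separate matter.

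**4. Precision of the early/late ratio.** Half-width = 2.101 × SE on the log10 scale.
- SD 0.26: 2.101 × 0.1163 = 0.244, a factor of 10^0.244 = 1.76 either way.
- SD 0.37: 2.101 × 0.1644 = 0.345, a factor of 2.22.

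**5. Chance of ruling out a loss if the groups are truly equal** (lower 95% limit above 1/margin)

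| Loss to rule out | SD 0.26 | SD 0.37 |
|---|---|---|
| 1.5-fold | 30% | 17% |
| 2-fold | 69% | 41% |
| 3-fold | 97% | 78% |

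**6. Carriers available.** At the plan's 50% colonisation rate, the chance that 22 inoculations give at least 11 carriers is 58% in one group and 0.584² = 34% in both. Fewer than 10 evaluable carriers in a group is therefore plausible.

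**The case against.** A reader might infer that the plan will treat p > 0.05 as proof of sufficiency. The document does not say so. Section 13.3 names two tests and stops; no section links either to the decision in 3.5. What can be said is that a non-significant result could be read that way and that nothing in the plan prevents it.

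Sufficient can also be read in absolute terms: enough response after short carriage, whatever happens after 14 days. The seroconversion hypothesis in 6.6, the rise from day 0 in 13.1, the 4-fold rise in 13.2 and the McNemar test in 13.3 all fit that reading. On it, success comes from rejecting a null, so the direction of inference is sound, and 10 carriers give over 99% power for a 4-fold rise on a continuous titre. This objection stands in part. But the within-group reading is not declared as the criterion, seroconversion has no threshold, and 4.1 and 13.1 still call for an early v late comparison. A significant rise in group 1 shows some response; it does not show how much is lost against 14 days.

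It would also be too strong to say that a material deficit would usually be missed. On log titre at SD 0.26, a 2-fold deficit is missed 31% of the time and a 3-fold deficit 3%. Missing it more often than not requires a smaller deficit, the larger SD for a 2-fold deficit, or Fisher's test with responder rates such as those assumed above.

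Finally, this is a small, unrandomised study meant to inform later work. That argues for a modest remedy, and against treating a non-inferiority margin as the only acceptable one.

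**Conclusion.** The concern holds in this form: the plan sets a sufficiency question and a primary early v late comparison, but provides only a test for a difference, with no interval, margin or definition of sufficient. A non-significant result at about 10 carriers per group would not exclude a material loss of response.

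How serious that is depends on the SD and on what loss counts as material, and the plan settles neither. At the present size the trial is well placed to exclude a 3-fold loss if 0.26 is the SD of the rise, less so for a 2-fold loss, and poorly placed for a 1.5-fold loss; each is weaker at SD 0.37. These figures rest on two-sided 5%, 10 evaluable carriers per group and, for Fisher's test, assumed responder rates. The point should be fixed. It does not invalidate the study, and better specification makes fuller use of data already planned.

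**What to change.** **In 13.3**
- Make the primary early v late analysis the ratio (group 1/group 2) of geometric-mean fold rises in serum IgG from day 0 among carriers, estimated from log10 titres with a 95% CI.
- Report it at both time points in 13.1 and name one as primary. Note that 28 days after eradication is day 32 in group 1 and day 42 in group 2, so time since inoculation differs there.
- Define sufficient before the data are seen. Either the lower confidence limit must lie above a margin the investigators justify, or group 1 must meet an explicit within-group criterion, reported alongside the ratio and its CI.
- State that a non-significant difference is not evidence of sufficiency.
- State that allocation by preference (5.3) limits the conclusion; an interval does not remove that confounding.

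**In 13.2**
- Say whether 0.26 is the SD of titres or of rises.
- Add the precision and power at the present size for both SDs: the CI factors in step 4 and the 2-fold and 3-fold rows of step 5 above.

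**Cost.** Wording in two sections and one definition to agree. No extra volunteers, visits or samples are needed. Some results that might have been described as showing no difference would be reported as inconclusive, and the stated 90% power would sit beside less favourable figures, such as those for a 2-fold loss.

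### Section 13.3 names only tests for yes/no data, so the titre analysis on which section 13.2 sizes the trial is missing from the analysis plan

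*Combined protocol and SAP*

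**What the plan says.** Section 13.1 defines the primary endpoint as "Rise in serological specific antibody titre comparing day 0 versus day 14 and 28 days post eradication", and also as a comparison of early with late eradication. Two secondary endpoints are of the same kind: the rise in mucosal titre, and "Change in nasal cytokine profile comparing day 0 versus day 4, 14 and 28 days post eradication". The colonisation and eradication endpoints in the same list are culture results, which are yes/no.

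Section 13.2 works on the log scale. It cites a previous challenge study: "This gave SDs on a log-10 scale of 0.11 for IgA saliva and 0.26 for serum total IgG". It then says that "using the SD of 0.26 we will be able to confirm a 4 fold rise with 10 carriers" of the organism "with 90% power using analysis of variance", and sets the target at "11 individuals colonised for each group up to a maximum of 22 volunteers for each group".

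Section 13.3 names who will do the analysis and then gives one sentence of method: "Differences between groups at each time point will be assessed using Fisher exact test and between time points within groups by McNemar test". It mentions no endpoint, no transformation, no significance level and no method for continuous data.

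Section 6.6 hypothesises seroconversion by day 14 in those colonised at day 4. Seroconversion is not defined there or elsewhere, and it is not listed as an endpoint.

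**The concern.** Fisher's exact test compares proportions between groups. McNemar's test compares a yes/no status at two times in the same people. Neither takes a titre or a cytokine concentration as input. Section 13.3 does not restrict them to the culture endpoints, and its two comparisons (between groups, and between times within a group) are also the two that the primary endpoint calls for. Sections 13.2 and 13.3 thus describe different analyses, and only 13.2's matches the endpoint.

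An analyst who follows 13.3 must either choose a titre cut-off or go outside the plan for the primary endpoint. Whichever is done would be decided after the plan was fixed, in a study that section 5.3 describes as neither randomised nor blinded. Section 3.5 says that the result will decide whether a short containment is enough for immunogenicity in the later work with the modified strain. A weak comparison of day 4 with day 14 eradication could then be read as showing no difference.

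**Working it through.** **Inputs.** From section 13.2: SD 0.26 on log10; 4-fold rise, log10(4) = 0.602; 10 carriers, recruited as 11 per group to allow for dropout. The plan does not say whether 0.26 is the SD of a titre or of a change, so two values of the SD of change are used: 0.26, and 0.26 × √2 = 0.37 (SD 0.26 at each time, uncorrelated). Assumed because not stated: two-sided 5%, and normally distributed log10 change.

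**The plan's own figure.** Power from the noncentral t distribution for a 4-fold rise:

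| Design | SD 0.26 | SD 0.37 |
|---|---|---|
| Paired, 10 carriers | >99.9% | 99.5% |
| Two groups of 10, 4-fold rise v no rise | 99.8% | 93.3% |

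The stated 90% is not reproduced with 10 per group; it is conservative. The nearest match with SD 0.26 and a 4-fold difference is two groups of 5 (89.2%), which is not the size that 13.2 applies. The point here does not depend on the 90%.

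**McNemar within a group, if titres are dichotomised.** Call a carrier a responder if the rise is at least c-fold, where c is an assumption. Nobody is a responder at day 0, so all changes go one way. With k responders the exact two-sided p-value is 2 × 0.5^k: k = 5 gives 0.063 and k = 6 gives 0.031, so at least 6 of 10 are needed.

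P(responder) = Φ((0.602 − log10 c)/SD), and power = P(Binomial(10, p) ≥ 6).

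| Cut-off c | p, SD 0.26 | Power | p, SD 0.37 | Power |
|---|---|---|---|---|
| 4-fold | 0.500 | 38% | 0.500 | 38% |
| 3-fold | 0.685 | 82% | 0.633 | 71% |
| 2-fold | 0.877 | 99.6% | 0.794 | 96% |

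A paired test on log10 titre has over 99.9% and 99.5%. At the 4-fold cut-off the result also depends on details: 11 carriers give 50%, and the uncorrected chi-square form of McNemar with 10 carriers gives 83%.

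**Fisher between groups.** This is the primary objective in section 4.1. The documents state no between-group difference to detect, so assume true rises of 4-fold and 2-fold, a difference of 0.602 − 0.301 = 0.301, with 10 per group and the same SD of change in both. Power is by exact enumeration of both binomials.

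| Cut-off c | Fisher, SD 0.26 | Fisher, SD 0.37 |
|---|---|---|
| 1.5-fold | 11% | 9% |
| 2-fold | 25% | 12% |
| 2.5-fold | 29% | 14% |
| 3-fold | 30% | 14% |
| 3.5-fold | 28% | 13% |
| 4-fold | 25% | 12% |
| 4.5-fold | 20% | 11% |
| 5-fold | 15% | 10% |
| **t-test on log10 change** | **69%** | **41%** |

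No cut-off tried recovers half of the t-test's power.

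**The case against.** The strongest reply is that 13.3 does not say antibody rises will be tested this way. It names no endpoint. Fisher and McNemar suit the culture endpoints, including group 2 at days 4, 7 and 14 and the swabs before and after ciprofloxacin, and 13.2 names analysis of variance in connection with titre. On that reading, 13.3 covers the yes/no endpoints and simply leaves out the titre method. This is a fair reading and cannot be ruled out. It does not remove the point: the primary endpoint then has no method in the analysis section, and the same correction is needed.

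The second reply concerns the 38%. A reader might infer that the plan tests antibody rises with 38% power and would usually miss a real 4-fold rise. The documents do not support that. In 13.2 the 4-fold rise is the effect to be detected, not a responder definition; using it as the cut-off when the true mean rise is also 4-fold makes half the carriers responders by construction. The figure also needs the exact form of McNemar and exactly 10 evaluable carriers, although the target is 11 and section 9.4 keeps withdrawn volunteers' data in the primary analysis. Nor is 4-fold the only candidate: seroconversion in section 6.6 suggests some yes/no serology outcome, and section 11.5 refers the IgG assay to previously described methods, which are not given. A cut-off there can be neither assumed nor excluded. All of this stands, so the 38% is one end of a range of illustrations.

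**Conclusion.** The gap is real and should be corrected before analysis. Section 13.3 contains no method that can be applied to the primary endpoint as 13.1 defines it, nor to mucosal titres or cytokines, and it does not match the analysis of variance in 13.2. That follows from the text alone and needs no assumption.

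The size of any power loss is conditional. Within a group, a true 4-fold rise could still be detected well by McNemar if the cut-off were low, so a large loss there is possible but not established. Between groups the loss is more consistent: for assumed rises of 4-fold and 2-fold, Fisher has at most about 30% against 69% (SD 0.26), or 14% against 41% (SD 0.37), over cut-offs from 1.5- to 5-fold. These figures rest on two-sided 5%, normal log10 change and 10 evaluable carriers per group. The importance of the point rests on the missing primary analysis and the undefined cut-off, not on any single power figure.

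**What to change.** Rewrite section 13.3 to say:

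- Fisher's exact test and McNemar's test apply only to the culture (yes/no) endpoints.
- Serum titre, mucosal titre and cytokines are analysed as continuous log10 values. Within-group change uses a paired or repeated-measures linear model, and early v late eradication uses the matching linear model, consistent with 13.2.
- Results are reported as geometric mean fold rises and their ratios between groups, with 95% confidence intervals.
- Any responder or seroconversion proportion uses a cut-off written into the plan in advance and is supportive only.

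In the same edit, state the significance level and whether 0.26 is the SD of a titre or of a change. The cost is a few sentences, with no extra samples, visits or volunteers.

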4.2 Secondary objectives

- To assess the efficacy of oral ciprofloxacin in eradicating nasal *Neisseria lactamica* colonisation by 24 hours after treatment

5. Description and justification of the study design

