11.4 Microbiological sampling

Estimates of population density will be measured at each sampling point. Positive colonisation will be defined as the culture of at least one isolate from day 4 onwards after inoculation (Deasy, Guccione et al. 2015). We will record the duration of positive colonisation and the effectiveness of eradication therapy in clearing colonisation in 24 hours.

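### The only within-group test named, McNemar, shows whether carriage changed, not how completely ciprofloxacin clears it at 24 hours

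*Combined protocol and SAP*

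**What the plan says.** Section 13.3 names two tests for the whole study. "Differences between groups at each time point will be assessed using Fisher exact test", and changes are assessed "between time points within groups by McNemar test". It gives no significance level, no version of McNemar, no analysis set and no confidence interval.

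The eradication endpoint in section 13.1 is throat-swab culture on the day of eradication and 1, 10 and 28 days later. That is a comparison between time points within a group, so McNemar is the test that falls to it. The objective it serves is the only one in section 4.2: "To assess the efficacy of oral ciprofloxacin in eradicating nasal" *N. lactamica* carriage, judged 24 hours after treatment. Section 3.5 gives the use: before designing the study of the genetically modified strain, the team needs to know "how quickly we can discharge the volunteers after ciprofloxacin eradication". Section 11.4 adds that the team will record "the effectiveness of eradication therapy in clearing colonisation in 24 hours".

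The sample size in section 13.2 rests on antibody titre alone. It has no calculation for eradication. The number of carriers comes from the statement that "we will therefore recruit volunteers until we have 11 individuals colonised for each group", up to 22 volunteers per group.

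**The concern.** The question behind the objective is how close 24-hour clearance comes to complete. Section 3.4 cites 100% clearance of *N. meningitidis* at 24 hours as the precedent. McNemar addresses a different null hypothesis: that as many volunteers turn from positive to negative as turn from negative to positive. Among volunteers who are positive on the day of treatment, change can go only one way, so rejecting that null says only that some clearance occurred. The test yields neither a clearance proportion nor a lower bound for one.

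A small p-value can therefore sit beside a clearance rate that is poor or very uncertain. A reader planning discharge in the later study needs the rate and its lower limit.

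**Working it through.** **Inputs.** Section 13.2 gives 11 colonised volunteers per group, from the statement that "we will be able to confirm a 4 fold rise with 10 carriers" plus an allowance of about 10% for dropout. The significance level is not stated, so two-sided 0.05 is assumed.

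**The plan's own figure.** 10 × 1.1 = 11, as stated (10 / 0.9 = 11.1 would round up to 12). This is the only denominator the documents offer for eradication.

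**McNemar among treatment-day carriers.** With k clearances and no reverse changes, the exact two-sided p-value is 2 × 0.5^k.

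- k = 5: 2 × 0.03125 = 0.0625, not significant.
- k = 6: 2 × 0.015625 = 0.031, significant.

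With 11 carriers the threshold is 6/11 = 54.5%. The Clopper-Pearson 95% interval is 23.4% to 83.3%, and five volunteers are still positive.

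**Other versions of the test.** The continuity-corrected form also needs 6 clearances (p = 0.041). Mid-p or one-sided exact needs 5 (5/11 = 45%). The uncorrected chi-square needs 4 (4/11 = 36%).

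**Chance of significance with 11 carriers.** P(at least 6 of 11 clear) is 0.50, 0.75 and 0.92 for true clearance of 50%, 60% and 70%.

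**If all inoculated volunteers are analysed.** With one negative-to-positive change:

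- 7 clearances: p = 2 × (1 + 8) / 2^8 = 0.070.
- 8 clearances: p = 2 × (1 + 9) / 2^9 = 0.039.

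The threshold rises to 8, which is 8/11 = 73% if there are 11 carriers.

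**Fisher does not fill the gap.** With 6/11 cleared in each group, Fisher gives p = 1.0. It compares the groups and says nothing about the level of clearance.

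**What an interval would show.** If all n carriers clear, the Clopper-Pearson lower 95% limit is 0.025^(1/n).

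| Cleared | Lower 95% limit |
|---|---|
| 10/10 | 69.2% |
| 11/11 | 71.5% |
| 10/11 | 58.7% |
| 22/22 (pooled) | 84.6% |
| 21/22 (pooled) | 77.2% |

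**The group 2 denominator.** Recruitment to group 2 stops on day 4 colonisation (synopsis; section 5.2), but treatment is on day 14 (section 10.1), so its carriers at treatment may be fewer or more than 11. As illustrations, 8/8 would give 0.025^(1/8) = 63.1% and 15/15 would give 0.025^(1/15) = 78.2%. The McNemar threshold stays at 6 clearances in both cases: 6/8 = 75% and 6/15 = 40%.

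**The case against.** Section 13.3 is one general sentence covering every comparison. A reader might infer that a significant McNemar result would be taken as proof of eradication or as permission to discharge. The documents do not say so: section 3.5 says the information will inform later designs, and no decision rule is attached to a p-value. A reader might also infer that no clearance result will be reported. Section 11.4 commits the team to recording 24-hour effectiveness, and a count such as 6/11 would look poor whatever the p-value. Both objections stand. What remains is that no denominator or interval is planned for that result.

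The threshold of about half is also conditional. Section 13.3 does not restrict McNemar to carriers, and section 10.1 assigns treatment by group and day, not by culture result. Section 3.4 says data on early detection are lacking, so a volunteer could turn positive between day 4 and day 5. One such change moves the threshold to 8. This stands as a limit on the figure, but the test still gives no clearance rate.

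Twenty-two carriers at treatment are not assured. Apart from the day 14 question, each group is capped at 22 volunteers. At the plan's 50% colonisation rate, the chance of at least 11 colonised out of 22 is 0.58.

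Finally, a reader might want to use untreated group 2 carriers, from day 4 to day 7 or day 14, as a ready control for spontaneous loss. Table 10.2 does not support a like-for-like comparison. Those intervals are 3 and 10 days, with windows of ±2 days on the later visits, against 1 day after treatment. Set beside the 24-hour rate without that caveat, they could overstate background loss.

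**Conclusion.** The point holds as a mismatch between test and objective. McNemar tests change, while section 4.2 asks for efficacy at 24 hours and section 3.5 wants it for discharge timing. The exact test would be significant at 6 of 11 cleared (p = 0.031; 95% interval 23% to 83%). That figure assumes a two-sided 0.05 level, analysis of treatment-day carriers only, and no reverse changes; one reverse change among all inoculated volunteers raises the threshold to 8. The conclusion itself does not depend on these assumptions, because no version of the test produces a clearance rate or a bound.

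The documents do not support the stronger reading that the plan would declare ciprofloxacin adequate from a p-value. The gap is in the pre-specified estimate and its precision, for a secondary objective. It should be closed, since it is the only secondary objective listed and has a stated use.

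**What to change.** In section 13.3, for the eradication objective, replace McNemar with the following.

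- **Estimate:** the proportion culture-negative at 24 hours among volunteers culture-positive on the day of eradication (day 4 in group 1, day 14 in group 2), with an exact Clopper-Pearson 95% interval. Report the same at 10 and 28 days.
- **Presentation:** per group, with the pooled figure as a supporting summary because the groups are treated after different periods of carriage.
- **Precision:** state in advance what each denominator can show (11/11 gives a lower limit of 71.5%; 22/22 gives 84.6%), and note that the number of group 2 carriers on day 14 may differ from 11.
- **Background loss:** do not use untreated group 2 loss as a direct comparator. If it is reported, label it descriptive and state its 3-day and 10-day intervals.

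The cost is a change of wording. All the swabs are already scheduled, and no volunteers, visits or samples are added. The downside is a slightly less favourable efficacy statement, since even complete clearance will carry a lower limit well below 100%.
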